The University of Texas Southwestern Medical Center at Dallas Institutional Review Board

PROJECT SUMMARY

Principal Investigator:

[name], PT, DPT, PhD

Study Title:

Scoliosis-Specific Exercises for At-Risk Mild AIS Curves: A Multi-Site Preliminary Randomized Trial

Sponsor/Funding Source:

Scoliosis Research Society

Purpose:

To investigate the feasibility and short-term effectiveness of scoliosis specific exercises as part of a multi-center randomized controlled trial in patients with mild AIS curves at the greatest risk of progression. Specifically, our study aims are as follows:

Aim 1: The primary aim is to assess the feasibility of a multi-site prospective randomized controlled trial in skeletally immature patients with mild AIS curves at high risk of progression. Participants instructed in scoliosis-specific exercises (SSE) provided by physical therapists certified in the Schroth-based method (SSE group) will be compared to the standard-of-care of observation (control group).

Feasibility will be evaluated according to participant:

1) recruitment rate at each site (measured by the number of participants enrolled per month at each site)

2) overall recruitment rate (measured by the total number of participants enrolled after 1 vear)

3) treatment attendance in the SSE group (measured by the percentage of prescribed hours of physical therapy sessions attended)

4) home exercise adherence in the SSE group according to weekly e-mails (measured by the percentage of prescribed exercises completed from baseline to 1 year)

5) home exercise adherence in the SSE group according to a smartphone application (measured by the percentage of prescribed exercises completed from baseline to 1 vear)

6) home exercise adherence in the SSE group according to an exercise log (measured by the percentage of prescribed exercises completed from baseline to 1 year)

Aim 2: The secondary aim is to assess whether scoliosis-specific exercises (SSE) will be more effective in skeletally immature patients with mild AIS curves at high risk of progression, Current Protocol 4.19.2019.docx

Page 1 of 13

compared to the standard-of-care of observation (control).

The outcome quantifying the effect of 1 year of physical therapy intervention will include:

1) curve magnitude (measured by the Cobb angle on radiograph at baseline and 1 year)

2) curve progression (measured by whether the curve progresses >5° after 1 year)

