Managing AIS can be considered a quality-of-life issue, since it does not result in premature death.³ Scoliosis may be associated with pain, torso deformity, psychological distress and pulmonary dysfunction.⁴ Bracing may result in decreased guality-of-life such as reduced activity and self-image, especially those with smaller curves.⁵ Patients commonly report discomfort with wearing a brace. Furthermore, most patients prescribed brace wear are not compliant.⁶ In contrast to bracing, exercise for AIS has been found to be emotionally satisfying⁷ and is the patient-preferred option.⁸ Furthermore, supervised Schroth exercises for AIS have been shown to significantly improve self-image according to the SRS-22 as compared to a control group.⁹ However, in North America, exercises are typically not offered to patients with smaller curves as part of the medical management of AIS. Exercise treatment during adolescence may prevent curve progression and its consequences, as less than 10% of curves kept below 29° at maturity continue to progress into adulthood.¹ At skeletal maturity, only 30% of curves greater than 30° continue progressing slowly, but 70% of the curves >50° progress at a rate of 1° per year.¹⁰ The negative consequences of progressive scoliosis most commonly manifest themselves once curves exceed 40-50°, justifying efforts to prevent progression.^{1,4} Furthermore, patients who are Risser 0 with mild curves are at a high risk of curve progression.¹¹ In a sample of 123 AIS patients with curves 10-49°, Bunnell (1986) reported a 68% risk of curve progression $\geq 10^{\circ}$ in patients who are Risser 0, and a 44% risk of curve progression ≥10° in patients with curves <20°.¹¹ In a sample of 727 JIS and AIS patients with curves 5-29°, Lonstein & Carlson (1984) reported a 38% risk of curve progression $\geq 10^{\circ}$ in patients who are Risser 0, and a 38% risk of curve progression $\geq 10^{\circ}$ in patients with curves <20° who are Risser 0-1.12 In a large cohort (sample size unknown) of AIS patients who are Risser 0 and 1, a 50% risk of curve progression ≥5° was found in patients with curves 15-30°.¹³

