lacking. Given the persisting uncertainty among medical professionals regarding the true potential of SSE, the purpose of this trial is to objectively and rigorously evaluate SSE compared to observation (standard-of-care). The results from this trial will provide much needed high-quality evidence regarding the feasibility and efficacy of SSE. In particular, this study will limit the inclusion criteria to skeletally immature patients with mild AIS curves. These patients are at highest risk of curve progression and have a greater potential for a meaningful effect with early intervention before their growth spurt and curve acceleration phase. Many families hope to avoid the need for bracewear.⁸ A smaller curve is more flexible²⁸ and may be more amenable to changes from exercise, especially before spinal growth is complete. In particular, mechanical wedging of the immature disc and vertebral body may still be reversible.²⁹

Concise Summary of Project:

This study will be a multi-center, dual-arm randomized control study evaluating skeletally immature patients with mild AIS curves. At six institutions, patients will be randomized into either the scoliosis-specific exercise (SSE) treatment arm or a control group. The SSE group will receive training in SSE, posture, and activities of daily living by physical therapists certified in Schroth-based exercise methods. The control group will not receive SSE instruction and will only be observed by their treating orthopaedic surgeon (which is considered the standard-of-care treatment method). Results will be compared after one year of treatment.

Study Procedures:

All patients with AIS meeting the following inclusion criteria will be eligible to participate in this trial: diagnosis of AIS; ages 10 to 17 years; major curve Cobb angles 12° to 24°; thoracolumbar, lumbar, or primary thoracic curve patterns; and Risser grade 0. Patients will be excluded according to the following exclusion criteria: scoliosis other than AIS, upper thoracic or double curve patterns, developmental disorders that prevent understanding and compliance with an exercise schedule, current or previous brace wear, and previous participation in a SSE program, previous spine surgery, inability to commit to performing a home exercise program for 15 minutes a day, 5 days a week, and inability to commit to attend at least 8 hours of PT within 6 months.

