Patient medical records will be reviewed for eligibility. If a patient is deemed eligible for inclusion in the study, a member of the research team will meet with the patient and his or her family to review the consent form in a private medical exam room. The family will be given ample time to review the consent form and ask any questions. If a participant chooses to participate, a consent form will be signed by both the patient and the legal guardian prior to any investigational procedures occurring.

Once a consent form has been signed, patients will be randomly assigned by the TSRH on site statistician to one of the two following groups:

1) Standardization of Physical Therapy:

Current Protocol 4.19.2019.docx Page 4 of 13 Physical therapists from Texas Scottish Rite Hospital, Boston Children's Hospital, Columbia University Medical Center, Norton Leatherman Spine Center, Johns Hopkins University, and Texas Children's Hospital who received training and certification in the Schroth-based (BSPTS) method have been recruited as members of the study team. Physical therapists at each institution will deliver a standardized exercise intervention.

2) Study Groups:

A) Scoliosis-Specific Exercise (SSE) Group

Each patient assigned to the SSE group will attend at least 8 hours of supervised exercise training led by a Schroth-based certified physical therapist over the course of 6 months. Ideally, patients will be seen for 7 sessions:

- 1) First session: 2 hours
- 2) Session 2: 1 hour (1 week later)
- 3) Session 3: 1 hour (1-2 weeks later)
- 4) Session 4: 1 hour (2-3 weeks after Session 3)
- 5) Session 5: 1 hour (3-4 weeks after Session 4)
- 6) Session 6: 1 hour (1-2 months after Session 5)
- 7) Session 7: 1 hour (1-2 months after Session 6)

The exact number of training sessions and time frame will be determined by the patient's ability to perform the exercises. All therapists will use a standardized exercise prescription algorithm and performance checklist similar to [name] scoliosis exercise study. Patients will perform a home exercise program for 15 minutes a day, 5 days a week, when they can independently execute their prescribed exercises according to the following criteria:

1) Correctly move the pelvis so the body weight is over the base of support and neutral.

2) Accurately set up exercises per curve pattern in different positions. Exercises progress from static to dynamic and passive to active corrections.

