3) Proficiently perform a minimum of 8 exercises integrating scoliosis-specific corrections which include auto-elongation to increase the spaces between the pelvis, vertebrae, and ribs. Various kinesthetic, mental imagery and proprioceptive strategies are used to further open concavities and depress convexities.

4) Perform scoliosis-specific corrections during activities of daily living. The overall goal is for patients to maintain a corrective posture throughout the day.

Patients will be asked to use a smartphone or tablet application (app) when performing the home exercise program which will be one method of tracking exercise adherence. A paper version of the app will be available to patients without access to a smartphone or tablet. Patients will also be sent electronically via email that is collected with a demographic intake form on the patient's initial visit, a weekly survey regarding home exercise adherence through a secure research database, the Research Electronic Data Capture (REDCap). An exercise log initialed by the guardian will help families keep track of their exercise adherence and serve as a way to monitor exercise adherence for patients who may not have a smartphone, tablet, or computer.

Current Protocol 4.19.2019.docx Page 5 of 13 Patients will also be able to meet with the therapists at their return-to-clinic visits and every 2-3 months thereafter until their 1 year follow-up to assess performance quality, maintain motivation, and progress intensity. Patients may be withdrawn if they do not maintainexercise adherence within 6 months.

B) Control Group

Patients randomized to this group will continue receiving standard-of-care treatment from their orthopaedic physician which includes regularly scheduled clinic visits and observation. Observation consists of no treatment of the scoliosis, only routine clinical assessment by the orthopaedic surgeon to detect curve progression every 3 to 6 months.

Once all measurements have been collected at the patient's enrollment and one year followup, patients in this group will continue to be tracked through observation until skeletal maturity in order to record whether the patient experienced curve progression, was prescribed a brace, or proceeded to surgical treatment.

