Patients randomized to the exercise group who never initiate physical therapy (do not attend even one session of physical therapy or begin a home exercise program) may be switched to the control group and observed in the same manner.

3) Outcome measures

Patients and their legal guardians will be asked to fill-out three self-reported outcome scores at their initial appointment and 1 year post the initiation of their participant in the study. The questionnaires to be completed include:

SRS-22:

The survey is a valid instrument for the assessment of the health related quality of life of patients treated for idiopathic scoliosis. This Heath Related Quality of Life (HRQL) questionnaire is designed to assess the effect that idiopathic scoliosis has on the patient in regards to pain, activity level, medications used, and satisfaction with treatment to date, and mental health status. The SRS-22 is one of the frequently tested scoliosis questionnaires and has been shown to have high levels of both reliability and validity.

Patient and parent survey:

A 3 question survey (one for patient, one for parent) that asks patients and parents questions regarding their/the child's attitudes toward SSE, their/their child's posture, and their/their child's scoliosis.

Once all measurements have been collected at the patient's enrollment at and one year follow-up, patients in this group will continue to be tracked through observation until skeletal maturity in order to record whether the patient experienced curve progression, was prescribed a braced, or proceeded to surgical treatment.

Current Protocol 4.19.2019.docx Page 6 of 13 While the SSE training will be considered for research purposes only, all regularly scheduled clinic visits with the patients' treating physicians and x-rays will be considered standard-of-care.

Anticipated Results:

We predict that at one-year follow-up:

I. A multi-site prospective randomized controlled trial in skeletally immature participants with mild AIS curves at high risk of progression is feasible as evidenced by acceptable participant recruitment rates (\geq 18 participants per site after 1 year), treatment attendance (\geq 80%), and home exercise adherence.

II. Scoliosis-specific exercises will be effective and will demonstrate:

- 1) Significantly smaller change in curve magnitude
- 2) Significantly reduced incidence of curve progression
- 3) Significantly reduced incidence of brace prescription

Criteria for Inclusion of Subjects:

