All patients diagnosed with Adolescent Idiopathic Scoliosis who meet the following inclusion criteria will be eligible to participate in this trial:

- 1) Age 10 to 17 years
- 2) Major curve Cobb angles of 12° to 24°
- 3) Compensatory curve should be less than 5° of the main curve (ex: 10° if the main curve is 15° or 15° if the main curve is 20°)
- 3) Risser Grade 0
- 4) Single thoracic, thoracolumbar, or lumbar curve patterns

Criteria for Exclusion of Subjects:

Patients will be excluded according to the following exclusion criteria:

- 1) Scoliosis other than AIS (congenital, neuromuscular, etc)
- 2) Upper thoracic or double curve patterns
- 3) Diagnosis of a developmental disorder that prevents understanding and compliance with an exercise schedule
- 4) Current or previous brace wear
- 5) Previous participation in a SSE program
- 6) Previous spine surgery
- 7) Patient inability to commit to attend at least 8 hours of PT within 6 months

Sources of Research Material:

Current Protocol 4.19.2019.docx Page 7 of 13 After the consenting process, patient demographics will be collected from the patient chart. All demographic information, clinical, and radiographic measurements will be recorded after informed consent is obtained during the patient's appointments.

Texas Scottish Rite Hospital will serve as the lead institution for this study and will create/maintain a REDCap database to house all study data. All other participating sites will obtain IRB approval from their own institutions and will enter into a Data Use Agreement contract with Texas Scottish Rite Hospital in order to access the database and run data analysis. Only a limited data set will be shared between the institutions, and all patient information will be entered into the database in a de-identified fashion. The data to be shared between institutions includes:

- Patient study number (to be generated for each institution in a de-identified format through REDCap)
- Date patient is consented to the study
- Date physical therapy/control status is initiated
- Age
- Initial curve Cobb angles
- Risser sign
- De-identified x-ray images (AP and Lateral views)
- Height, Weight, and BMI
- Physical activity level
- Curve pattern (classification as thoracic, thoracolumbar, or lumbar)
- Schroth curve pattern
- Trunk rotation
- Triradiate status
- Menarchal status
- SRS-22
- 3 question parent survey about attitudes toward SSE, posture, and scoliosis

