All information obtained through medical and radiographic records will be reviewed solely by the primary investigators, co-investigators, and other study team personnel. Publically reported information will be in the form of a statistical summary only: no information will be divulged that could be linked to a specific patient involved with the study. No patient information will be disclosed outside of the study team. The University of Texas Southwestern Medical Center Institutional Review Board may review the research information for auditing purposes. The team will keep the consents and study files in both a locked cabinet as well as electronic copies within the electronic study folder (this folder will be stored on password encrypted hard drive which may be accessed by members of the study team only). All other electronic data collected will be stored on a password protected electronic database with access limited to the study team.

Procedures to Maintain Confidentiality:

All normally used means for protecting patient confidentiality will be strictly followed. All consents, clinical and radiographic measurements, and patient demographics will be stored in a secure electronic database. This database will be password protected and access will be limited to only individuals on the study team. Data will be de-identified for each patient by assigning a Study ID in the database. All PHI and the unique study ID for each patient will be stored in a separate password-protected and encrypted spreadsheet that only members of the study team at TSRH will have access to. Only a statistical summary of the information will be published: at no time will any data published include information that can be linked to a study participant. All requirements for HIPAA compliance in regards to patient confidentiality will be followed and the University of Texas Southwestern Medical Center's Institutional Review Board will have the right to inspect all medical records related to this study for the purpose of ensuring patient confidentiality.

Current Protocol 4.19.2019.docx Page 10 of 13

Biostatistics

Continuous variables will be summarized with means, standard deviations and ranges and analyzed using student t-tests; categorical variables will be summarized as counts and percentages and analyzed using Fischer's exact tests. Data will be checked for normality and equal variance.

Potential Benefits:

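### Patients randomised to exercise who never start may be moved to the control group, and nothing requires analysis as randomised

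*Combined protocol and SAP*

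**What the plan says.** The rule stands in the combined protocol and SAP under Study Procedures, 2) Study Groups, B) Control Group. It covers patients randomised to SSE who attend no physical therapy session and begin no home programme. They "may be switched to the control group and observed in the same manner".

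Aim 1 defines its third measure as "treatment attendance in the SSE group (measured by the percentage of prescribed hours of physical therapy sessions attended"), and its three home-adherence measures are likewise taken in the SSE group. These are four of the six Aim 1 measures. Anticipated Results sets attendance of at least 80% as evidence of feasibility and gives no figure for home adherence.

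The Biostatistics section says: "Continuous variables will be summarized with means, standard deviations and ranges and analyzed using student t-tests". It adds Fisher's exact tests for categorical variables and checks of normality and variance. It names no analysis population, and no section says that patients are analysed in the group to which they were randomised.

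Two further places bear on the point. The SSE Group section says: "Patients may be withdrawn if they do not maintainexercise adherence within 6 months"; no analysis rule follows. The list of shared data items under Sources of Research Material includes "Date physical therapy/control status is initiated" but no item for the randomised group.

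**The concern.** The switch is discretionary, runs in one direction only, and is made after allocation is known. No time limit is set for deciding that a patient has never started, while control-type follow-up assesses the curve every 3 to 6 months. Nothing prevents a switch after progression has been seen.

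For Aim 1, failure to start is one of the things a feasibility trial exists to measure. Each non-starter who leaves the SSE group takes a zero out of the attendance figure, so a trial could meet its 80% criterion only because those who did not take up the treatment were no longer counted.

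For Aim 2, moving patients between arms on the basis of their behaviour after randomisation makes the comparison of Cobb angle, progression and brace prescription non-randomised. Any difference then mixes the effect of exercise with the prognosis of patients who do not start it.

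**Working it through.** The plan states no sample size, alpha or power, so it has no figure of its own to reproduce. The calculations below are illustrations.

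**Inputs from the plan**
- At least 18 participants per site (Anticipated Results), six sites (Concise Summary) and 2:1 allocation (Recruitment Methods). This gives 18 × 6 = 108, or 72 SSE and 36 control.
- Each SSE patient "will attend at least 8 hours of supervised exercise training"; the listed sessions total 2 + 6 × 1 = 8 hours.
- Progression risk: Background cites "AIS patients who are Risser 0 and 1, a 50% risk of curve progression" of 5° or more, in curves of 15–30°. It is used here as an assumption only. The trial enrols 12–24° curves at Risser 0 and counts progression above 5° at one year.

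**Assumptions not in the plan**
- The number of non-starters, *k*, and their own progression risk, *r*.
- The starters' mean attendance, *s*.
- The 80% criterion read as the SSE group mean.
- Two-sided alpha of 0.05.

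**Attendance.** With equal planned hours and non-starters at 0%, attendance as randomised = *s* × (72 − *k*)/72.

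| Starters' mean | Last *k* meeting 80% | First *k* missing 80% |
|---|---|---|
| 85% | 4: 0.85 × 68/72 = 80.3% | 5: 0.85 × 67/72 = 79.1% |
| 90% | 8: 0.90 × 64/72 = 80.0% | 9: 0.90 × 63/72 = 78.8% |
| 95% | 11: 0.95 × 61/72 = 80.5% | 12: 0.95 × 60/72 = 79.2% |

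The result flips at 5, 9 or 12 of 72 (6.9%, 12.5% or 16.7%). After switching, the reported figure stays at 85%, 90% or 95% whatever *k* is.

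**Aim 2, progression.** Assume no true effect and overall risk *p* = 0.50 in both randomised arms. After switching, the SSE arm has 72 − *k* patients at risk (72*p* − *kr*)/(72 − *k*). The control arm has 36 patients at risk *p* plus *k* patients at risk *r*. For example, with *k* = 7 and *r* = 0.80, SSE is (36 − 5.6)/65 = 46.8% and control is (18 + 5.6)/43 = 54.9%, a spurious gap of 8.1 points. The chance of a two-sided Fisher p ≤ 0.05 was found by exact enumeration; as randomised (*k* = 0) it is 4.0%.

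| *r* | *k* = 4 | *k* = 7 | *k* = 14 |
|---|---|---|---|
| 0.50 | 4.4% (no gap) | 4.3% (no gap) | 3.4% (no gap) |
| 0.65 | 5.0% (2.4 points) | 6.1% (4.1 points) | 9.6% (7.8 points) |
| 0.80 | 6.7% (4.8 points) | 11.4% (8.1 points) | 30.6% (15.6 points) |

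The gaps in the last two rows favour SSE. With *r* = 0.35 or 0.20 the gaps and two-sided rates are the same as for 0.65 and 0.80, but the gaps run against SSE, and false positives favouring SSE are 1.2% or less.

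The picture does not depend on *p* = 0.50. With *p* = 0.38 (a Background figure for progression of 10° or more) the rate is 3.7% as randomised. For *k* = 4, 7 and 14 it is 4.7%, 6.2% and 10.4% at *r* = 0.53, and 6.4%, 12.0% and 33.3% at *r* = 0.68.

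**The case against.** The strongest reply is that the sentence is permissive and sits beside the description of control follow-up. It could mean only that non-starters are seen on the control schedule, with the analysis still by randomised arm. That reading is possible, but no section secures it, and the words about switching to the control group point the other way.

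Several narrower objections stand in part:
- Only attendance has a numerical threshold, so no pass or fail result can flip on home adherence. The recruitment measures are unaffected.
- Home exercise begins only once a patient can perform the exercises independently, so a non-starter may have no prescribed exercises at all. Adherence would then be undefined rather than zero. This is a reason to fix the denominator in advance.
- Non-starters may be few, because the exclusions include "inability to commit to attend at least 8 hours of PT within 6 months". Study Procedures also excludes inability to commit to home exercise, although the separate exclusion list omits that item. With fewer than 5 non-starters none of the attendance scenarios flips, and 4 switched patients at 65% risk leave the false-positive rate at 5.0%. The case of 14 switched at 80% risk is extreme.
- The shared-data list may not be exhaustive, and the allocation list held by the lead site's statistician would allow the randomised group to be recovered.
- Efficacy is the secondary aim of a preliminary trial, and the Cobb angle comparison was not quantified here.

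These points limit the size of the problem. They do not supply the missing analysis rule.

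**Conclusion.** The concern holds and should be corrected before analysis. The plan contains an explicit rule for moving SSE non-starters to control and no rule keeping them in the SSE group for analysis.

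The upward direction for attendance is certain once non-starters are scored as zero of the planned hours, and home adherence behaves in the same way under that scoring. Whether the 80% criterion is affected depends on numbers the plan does not give: at 72 SSE patients it takes 5, 9 or 12 non-starters for starter attendance of 85%, 90% or 95%.

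For Aim 2, the loss of the randomised comparison is definite if switched patients are counted as controls. The size and direction of the resulting bias are not known: none at equal risk, in favour of SSE if non-starters have a worse prognosis, and against it if they have a better one. The conclusion rests on the absence of an as-randomised rule and not on any one of these scenarios.

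**What to change.** In the Control Group section, replace the switching sentence with wording to this effect:

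*Patients randomised to SSE who never initiate therapy may be observed on the control visit schedule but remain in the SSE group for all analyses. They count as 0% attendance, with the planned 8 hours as denominator, and as zero home exercise against the planned 15 minutes a day, 5 days a week.*

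A non-starter scores zero in minutes or in exercises, so the choice of unit does not matter for these patients.

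In Biostatistics, add:

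*All Aim 1 and Aim 2 analyses are by group as randomised, including patients withdrawn for non-adherence as far as data are available. Analysis by treatment received is supplementary.*

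For withdrawn patients, the same section should also state the adherence denominator after withdrawal and how a missing one-year outcome is handled.

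Add the randomised group, and the date and reason of any switch or withdrawal, to the shared-data list.

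The cost is a few sentences and a few database items, with no extra patients or visits. The attendance and adherence figures may come out less favourable.

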I am a [researcher or physical therapist] from Scottish Rite Hospital for Children. I'm calling you because I wanted to tell you about an opportunity to participate in a study that is looking at what happens to small curves and whether physical therapy exercises can slow the progression of the curve. Patients in this study are assigned randomly, like a flip of a coin, to one of two groups: a group that does exercises and a group that does not do exercises but only receives standard observation by the physician. You have twice the chance of being assigned to the exercise group. The group that does exercises is asked to do exercises 15 minutes a day, 5 days per week for one year. If you decide to participate, whether you are ^{Current Protocol 4.19.2019.docx} Page 9 of 13

assigned to the exercises group or the observation group, there is a \$200 stipend paid to you at the end of one year. You can choose to stop participating for any reason at any time, and this will not affect the way you are treated. We will also keep your health information confidential. Does this sound like something you are interested in getting more information about at your next visit?

If the family and patient are interested in participating in the study, the patient and family will be invited to return to the hospital for consent. The patient will then be consented according to the format listed above and be given ample time for questions and review. If the patient is not interested in participating in the study, they will be thanked for their time and a note will be made in the research documents that the patient declined participation.

Potential Risks:

Identifiable risks associated with participation in this study would be a potential loss of confidentiality and tired or sore muscles from the exercises.

Subject Safety and Data Monitoring

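### No feasibility measure follows the control arm after enrolment, so control loss or control uptake of exercise could not count against feasibility

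*Combined protocol and SAP*

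**What the plan says.** Purpose, Aim 1 makes feasibility of a multi-site randomised trial the primary aim and opens its list with "Feasibility will be evaluated according to participant". Six measures follow:

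- Measure 1: "recruitment rate at each site (measured by the number of participants enrolled per month at each site".
- Measure 2: "overall recruitment rate (measured by the total number of participants enrolled after 1" year.
- Measure 3: "treatment attendance in the SSE group (measured by the percentage of prescribed hours of physical therapy sessions attended".
- Measures 4 to 6: home exercise adherence in the SSE group from baseline to 1 year, by weekly e-mail, by app and by paper log.

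Anticipated Results, I predicts that such a trial "is feasible as evidenced by acceptable participant recruitment rates" and repeats these domains: at least 18 participants per site after 1 year, attendance of at least 80%, and home adherence with no figure attached.

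Aim 2 compares the arms at 1 year on Cobb angle, progression and brace prescription. For controls, Study Groups, B says "Observation consists of no treatment of the scoliosis, only routine clinical assessment" by the surgeon. Previous participation in an SSE programme is an exclusion at entry. Biostatistics gives summaries, t-tests and exact tests, with no dropout allowance and no plan for missing outcomes.

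**The concern.** A feasibility trial should show whether the definitive trial could be run and would answer its question. For SSE against observation over one year, that needs enough children enrolled, exercise delivered, outcomes obtained in both arms, and a control arm that stays largely unexercised. The stated measures cover the first two needs. The other two are covered, at most, by indirect signs in the SSE arm.

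A control counts fully towards recruitment on the day of enrolment and is not looked at again for feasibility. If many controls leave, or obtain similar exercise elsewhere, the stated evidence would still read as feasible. A later trial could then be planned without a retention or contamination allowance. Uptake by controls would also shrink the Aim 2 difference, possibly without anyone knowing.

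**Working it through.** **1. Which failures can each measure detect?**

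| Measure | SSE-arm loss | Control loss | Control uptake of SSE/PT |
|---|---|---|---|
| 1-2 Recruitment | no | no | no |
| 3 Attendance | partly | no | no |
| 4-6 Home adherence | partly | no | no |

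The two control columns follow from the definitions: enrolment is fixed at entry, and the other four measures are confined to the SSE group.

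The SSE column says partly for these reasons:
- Adherence runs from baseline to 1 year, so a lost child lowers it if kept in the denominator. The denominator is not stated, and adherence has no pass mark.
- Children who do not maintain adherence may be withdrawn, and those who never start may be moved to control.
- The supervised hours are planned over 6 months (2 + 6 x 1 = 8 hours), so later loss need not affect attendance. The protocol does not say whether later therapist meetings count as prescribed hours.

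Example of the denominator effect (assumed figures): if 14 of 72 never attend and 58 attend 90%, attendance is 58 x 0.90 / 72 = 72.5% of all randomised, which fails the 80% bar. It is 90% among those kept, which passes.

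**2. Size at the stated recruitment bar.** The bar has no stated derivation, so there is no figure to reproduce. Six sites (Concise Summary) x 18 (Anticipated Results, I) = 108. At 2:1 (Recruitment Methods) that is 72 SSE and 36 control.

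**3. Control loss (assumed 13 of 36).**
- Recruitment is still 108 of 108.
- With x braced among the 23 known, the control brace percentage lies between x/36 and (x + 13)/36, a width of 13/36 = 36.1 points.
- Control retention is 23/36 = 63.9%. With no SSE loss, pooled retention is (72 + 23)/108 = 88.0%, so a pooled figure would hide the problem.

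**4. Control uptake (assumed share c, full benefit).** The true difference becomes (1 - c) times its size, so 10% to 30% uptake shrinks it by 10% to 30%.

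**5. Effect on a comparison of proportions.** Assumed: 50% v 25% progression, two-sided 0.05. The 50% is borrowed from a cohort in Background (progression of at least 5 degrees, curves 15-30 degrees, Risser 0-1). The 25% and the alpha are assumptions. Normal-approximation power for two proportions:

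| Scenario | SSE/control | Power |
|---|---|---|
| No loss, no uptake | 72/36 | 73.5% |
| 25 controls remain | 72/25 | 63.5% |
| 18 controls remain | 72/18 | 54.1% |
| 10% uptake (47.5% v 25%) | 72/36 | 65.0% |
| 20% uptake (45% v 25%) | 72/36 | 55.7% |
| 30% uptake (42.5% v 25%) | 72/36 | 46.0% |

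For a definitive trial with 80% power on the same assumptions, total N rises from 129 with no uptake to 156, 195 and 252 at 10%, 20% and 30% uptake.

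**6. Could this trial measure retention usefully?** Exact (Clopper-Pearson) 95% intervals at about 80% retention: 87/108 overall gives 71.8% to 87.5%; 29/36 in the control arm gives 64.0% to 91.8%. The control figure is coarse, but enough to reveal a serious problem.

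**The case against.** Several points on the other side stand.

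- **Retention has support.** A $200 stipend is paid in either group at the end of one year, controls are seen every 3 to 6 months, clinic visits and x-rays are standard of care, and tracking continues to skeletal maturity. These make heavy loss less likely. They do not measure it.
- **Loss would be visible.** Missing 1-year films would show in the Aim 2 counts. But no bar is attached to them, and one chosen after the counts are known carries little weight.
- **Anticipated Results is worded as a prediction**, with no go/no-go decision. True, but it is the only statement of what would show feasibility, and the Aim 1 list has the same gap.
- **The choice of domains in a preliminary trial is partly the investigators' judgement.** That limits the severity, not the substance.

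Three stronger readings are tempting and not supported:

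- A reader might infer that loss in either arm is invisible. In the SSE arm it can lower the adherence measures.
- A reader might infer that controls are likely to leave because Background says exercise "is the patient-preferred option". That sentence contrasts exercise with bracing, not with observation. Background also says exercise is seldom offered for small curves in North America, which makes outside uptake less likely. The line "You can choose to stop participating for any reason at any time" in the phone script is ordinary voluntary-participation wording and follows directly on the stipend.
- A reader might infer that outside SSE will certainly go unrecorded. The list in Sources of Research Material covers only data shared between institutions and also omits brace prescription, an Aim 2 outcome, so it is not exhaustive. What can be said is that no such item is planned in that list or in the survey as described. General physical activity level is the nearest.

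**Conclusion.** The point holds for the control arm. Nothing in Aim 1 or Anticipated Results, I responds to control loss before the 1-year film or to controls taking up SSE or PT outside the trial, so the primary question could be answered favourably when either has failed. For the SSE arm the gap is partial and turns on an unstated denominator and an adherence measure without a pass mark.

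The size is illustrative only. The 36-point uncertainty rests on an assumed 13 of 36 controls lost at the 108 implied by the recruitment bar. The power and sample-size figures rest on assumed progression rates, alpha and uptake. The documents give no basis for predicting actual loss or uptake, and none of these figures should be read as expected. It is a cheap improvement: worth making because it bears on the primary aim, without invalidating the measures already there.

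**What to change.** Add two measures to Aim 1 and to Anticipated Results, I.

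(a) **1-year retention in each arm**: the number with a 1-year film and known brace status, divided by all randomised to that arm, so that withdrawn and switched children stay in their randomised arm's denominator. The investigators set the bar before the data are seen and require it in each arm separately. Add brace status to the shared-data list so that the numerator can be formed centrally.

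(b) **Outside exercise in controls**: the percentage of controls reporting any SSE or PT for scoliosis, from one question added to the existing 1-year patient and parent survey. Ask it at withdrawal too where possible, since a 1-year survey misses those who leave. Pre-set an acceptable maximum and report the figure beside the Aim 2 comparison.

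Neither threshold can be derived from the documents; both are for the investigators to choose. The cost is protocol wording, one survey question and one shared data item. The downside is that the feasibility criterion becomes somewhat harder to meet.
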